7.9.3.1.2 Gender Analysis

Assessment of the possible gender differences will be examined in the freedom from (or event rate) valve-related adverse events and death after implantation of the Model 400 valve.

The possible gender differences in the event rates of death and valve-related adverse events will be evaluated using the log-rank test.

Differences in gender will be considered to be significant if the p-value<0.05.

Revision 7.0

Page 21 of 22

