7.1.2.1 Endpoints

The effectiveness endpoints are

- NYHA Functional Classification (at discharge (up to 30 days), 3-6 months, 1 year and annually thereafter through 5 years)
- Hemodynamic Performance (at discharge (up to 30 days), 3-6 months, 1 year and annually thereafter through 5 years) including
 - effective orifice area (EOA)
 - effective orifice area index (EOAI)
 - peak pressure gradient
 - mean pressure gradient
 - valvular regurgitation
 - performance index
 - cardiac output
 - cardiac index

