7.5 Adjustments for Multiple Comparisons

There are no planned multiple comparisons expected and thus no multiplicity adjustments are planned for this study.

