7.9.3.1 Safety Endpoints

The safety endpoints include the valve-related adverse events of Thromboembolism, PVL, reoperation, explant and all-cause mortality. Events that occurred in less than five subjects will not be evaluated by the additional analyses.

The additional safety endpoint analyses described in Section 7.9.3.1 will be included in regulatory submissions to all geographies except for Risk Factor Analysis which will be included only in the submission in US.

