7.9.3.1.1 Valve Size Analysis

The evaluation of the effect of valve size over time to the valve-related adverse events and death will be performed as follows:

Cox Proportional Hazards model will be used to evaluate the valve size effect on valve-related adverse events and death.

Due to possible small sample sizes in the smallest and largest valve sizes, the 17 mm may be combined with the 19 mm and the 27 mm may be combined with the 29 mm size to create larger groups of valve sizes. Thus, four indicator variables for valve size (representing 17 mm to 19 mm, 21 mm, 23 mm, 25 mm, and 27mm to 29 mm) may be created and included in the model.

Valve size will be considered to be significantly associated with time to valve-related adverse events and death if the p-value <0.05.

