7.9.3.2.2 Gender Analysis

The NYHA classification will be summarized by gender and time intervals. The chisquared test will be used to evaluate the possible relationship between NYHA classification and gender at different time intervals.

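### Up to ten valve-size and gender safety tests are each declared significant at unadjusted p<0.05, with no exploratory label, while SAP 7.5 says no multiple comparisons are planned

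*SAP*

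**What the plan says.** SAP 7.9.3 (Additional Analyses) names the outcomes in 7.9.3.1: "The safety endpoints include the valve-related adverse events of Thromboembolism, PVL, reoperation, explant and all-cause mortality". It then applies a filter: "Events that occurred in less than five subjects will not be evaluated by the additional analyses".

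Two subsections attach a threshold to these outcomes:

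- SAP 7.9.3.1.1, Cox model: "Valve size will be considered to be significantly associated with time to valve-related adverse events and death if the p-value <0.05".
- SAP 7.9.3.1.2, log-rank test: "Differences in gender will be considered to be significant if the p-value<0.05".

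SAP 7.9.3.1 adds that its analyses "will be included in regulatory submissions to all geographies"; only the risk factor analysis is restricted to the US submission.

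SAP 7.9.3.2.2 adds a chi-squared test, "used to evaluate the possible relationship between NYHA classification and gender at different time intervals". It gives no threshold and does not say what result would count as significant.

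SAP 7.5 expects no multiple comparisons and concludes that "no multiplicity adjustments are planned for this study". Nothing in 7.9.3 orders the tests or calls them exploratory.

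**The concern.** The two sentences are decision rules, not descriptions. They fix in advance that a p-value below 0.05 on any one endpoint is a significant size or gender association, and the result then goes to regulators. A single test at 5% gives a false signal in one null trial in twenty; ten such tests give one far more often. A reader of the submission would have no statement of how many tests were run or how often chance alone would produce such a finding.

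The SAP shows elsewhere that it can make the distinction. Section 7.3 uses the word exploratory, 7.9.3.2.1 only summarizes hemodynamics by valve size, and 7.9.2.2 states that effectiveness has no formal hypothesis. Protocol 7.3.3 promises only an evaluation of possible gender differences, so the significance rule is the SAP's own addition.

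At stake is how a size or gender result may be described. The trial's primary conclusion is not at stake.

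**Working it through.** The documents give no familywise error rate for these tests, so there is no planned figure to reproduce.

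**Inputs from the SAP**
- Threshold: 0.05 per test (7.9.3.1.1 and 7.9.3.1.2).
- Endpoints: five (7.9.3.1), each tested once by size and once by gender. Maximum number of tests: 5 + 5 = 10. The five-subject filter works event by event, which fits testing each endpoint separately.
- An endpoint removed by the filter takes two tests with it, so the count goes 10, 8, 6.
- Adjustment: none (7.5).

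**Independent tests.** Chance of at least one p<0.05 when nothing is true: 1 − 0.95^k.

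| Tests run (k) | Calculation | Chance |
|---|---|---|
| 10 | 1 − 0.95^10 | 40.1% |
| 8 | 1 − 0.95^8 | 33.7% |
| 6 | 1 − 0.95^6 | 26.5% |

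**Allowing for correlation.** Endpoints overlap (explants are a subset of reoperations, and patients share risk), so a trial with no size or gender effect was simulated, 1,500 runs per scenario. It used a five-group log-rank (Cox score) test for size and a two-group log-rank test for gender.

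Assumptions that the documents do not give:
- 1300 subjects followed for five years in the base case;
- 25% women (50% in one scenario);
- size groups of 6/20/37/27/10%;
- annual rates of 2.5% thromboembolism, 1.2% PVL, 0.8% reoperation and 3% death;
- 70% of reoperations being explants.

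| Scenario | At least one false finding among the safety tests |
|---|---|
| Base case | 37.9% |
| Size and gender correlated (latent 0.6) | 36.1% |
| 50% women | 38.2% |
| Stronger shared risk, size and gender correlated | 37.3% |
| Almost no shared risk | 38.1% |
| 900 subjects, 1.5 years | 33.0% |

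The Monte Carlo standard error is about √(0.38 × 0.62 / 1500) = 1.3 percentage points. In the last row the filter sometimes removes an endpoint, so slightly fewer than ten safety tests are run on average.

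**Consistency of the SAP.** Section 7.5 expects no multiple comparisons; sections 7.9.3.1.1 and 7.9.3.1.2 plan up to ten. Both cannot stand as written.

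**The case against.** **These are additional analyses.** They sit apart from the formal safety hypothesis in SAP 7.9.1.2, the sample size does not rest on them, and no approval, success or stopping rule uses them. Protocol section 7 allows further exploratory work. This stands and limits the point to interpretation. It does not cancel an explicit rule on what will be called significant.

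**Strict error control is unwise in a safety screen.** A missed signal also matters, and the SAP's other screens use 0.15. This stands against making adjustment compulsory. With an assumed gender hazard ratio of 2 and 25% women (Schoenfeld approximation), moving from p<0.05 to p<0.01 cuts power from about 38% to 18% at 30 events, and from 81% to 61% at 90. It is no argument against an exploratory label.

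**Stronger readings that the documents do not support**
- A reader might count 17 tests by adding NYHA class by gender at seven visits; Protocol 7.1.2.1 lists "NYHA Functional Classification (at discharge (up to 30 days), 3-6 months, 1 year and annually thereafter through 5 years". Seventeen independent tests would give 1 − 0.95^17 = 58.2%. But SAP 7.9.3.2.2 attaches no threshold to the NYHA tests, so the p<0.05 rule covers ten at most.
- A reader might infer that the NYHA tests also go to all regulators. The submission sentence covers 7.9.3.1 only. The PMA cutoff, at the first date with 800 patient-years (SAP 7.2.2.1), would also leave late visits with little or no data in that report.
- A reader might take any of the four valve-size indicators as enough, giving 4 × 5 + 5 = 25 tests and up to 72% if independent. SAP 7.9.3.1.1 refers to valve size as one factor with one p-value, so a single overall test is the more natural reading. The wording is loose enough to merit stating it.

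**Conclusion.** The point holds for the valve-size and gender safety tests. With no true effect, the chance of at least one significant finding is about 36-40% if all ten tests are run. The upper end is exact under independence; the lower end rests on the simulation's assumed event rates, size mix and five-year follow-up. Shorter follow-up gave 33%, and fewer qualifying endpoints lower it further. Even at six independent tests it is over five times the 5% attached to each.

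The OPC tests and their type I error are unaffected. Nor do the documents tie any labelling claim or clinical action to a subgroup p-value; a reader might infer one, but it is not there. The defect is an unqualified significance rule that conflicts with SAP 7.5. It should be corrected, though it does not threaten the trial's main result.

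**What to change.** 1. Delete the sentences in SAP 7.9.3.1.1 and 7.9.3.1.2 that declare significance at p<0.05.
2. Label the size and gender analyses in 7.9.3 exploratory, including the NYHA-by-gender chi-squared tests in 7.9.3.2.2.
3. Report hazard ratios or differences with 95% confidence intervals and nominal p-values. For valve size, name the single overall test (four degrees of freedom with five size groups) as the source of the p-value.
4. Reword SAP 7.5 to say that these subgroup tests are exploratory and not adjusted for multiplicity.

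Holm within each five-test family is an option if the sponsor wants to keep significance language. It holds the error at 5% per family, so at most about 10% over the two. The smallest p-value would then have to reach 0.05/5 = 0.01, with the loss of power described above. It is not required.

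The cost is SAP wording only, with no change to data, patients or the primary analysis. The one thing given up is that a subgroup p<0.05 can no longer be reported as a significant association.

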7.9.3.1.3 Risk Factor Analysis

Risk factors associated with time to death (all causes), reoperation and explant will be evaluated using Cox Proportional Hazards model.

Variables evaluated as possible risk factors for death (all causes), valve-related reoperation and explant include age at implant, gender, preoperative NYHA classification, previous aortic valve replacement, valve size, and concomitant CABG. Other important concomitant procedures may also be included in this analysis.

A backwards elimination process will be utilized to pare the model down. In this process, the single-term baseline variable with the highest p-value will be removed from the model until all factors have a p-value less than 0.15.

7.9.3.2 Effectiveness Endpoints

The effectiveness endpoints include mean gradient, effective orifice area, valvular regurgitation and NYHA classification.

7.9.3.2.1 Valve Size Analysis

Mean gradient, effective orifice area and valvular regurgitation at one year postoperative will be summarized by valve size.

7.9.3.2.2 Gender Analysis

The NYHA classification will be summarized by gender and time intervals. The chisquared test will be used to evaluate the possible relationship between NYHA classification and gender at different time intervals.

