6.2 NYHA Functional Classification

The New York Heart Association (NYHA) Functional Classification is a system for defining cardiac disease and related functional limitations into four broad categorizations as defined in Table 3.

Table 3: New York Heart Association (NYHA) Classification

Class I	Subject with cardiac disease but without resulting limitations of physical activity. Ordinary physical activity does not cause undue fatigue, palpitation, dyspnea, or anginal pain.
Class II	Subjects with cardiac disease resulting in slight limitation of physical activity. They are comfortable at rest. Ordinary physical activity results in fatigue, palpitation, dyspnea, or anginal pain.
Class III	Subjects with cardiac disease resulting in marked limitation of physical activity. They are comfortable at rest. Less than ordinary physical activity causes fatigue, palpitation, dyspnea, or anginal pain.
Class IV	Subjects with cardiac disease resulting in inability to carry on any physical activity without discomfort. Symptoms of cardiac insufficiency or of the anginal syndrome may be present even at rest. If any physical activity is undertaken, discomfort is increased.

NYHA classification will be assessed at baseline, discharge (up to 30 days), and all in-office follow-up visits, and the results recorded on the appropriate eCRF. The NYHA classification should be assessed by a medical doctor, physician assistant or nurse practitioner.

6.3 12-Lead ECG

A standard 12-Lead ECG should be taken at baseline, discharge (up to 30 days), and all in-office follow-up visits to assess cardiac rhythm, noting any cardiac arrhythmias and indications for pacing. The site will record ECG data on the appropriate eCRF.

The Investigator or Sub-Investigator should review and sign/date each 12-lead ECG recording conducted as part of the trial requirements, verify or correct any automated diagnosis generated by the ECG machine, and note the clinical significance of any diagnosis/finding of the ECG. Any new abnormalities should be recorded on an Adverse Event eCRF.

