5.2 Exclusion Criteria

- 1. Patients who meet any of the following criteria will not qualify for participation in the trial. Patient has a pre-existing prosthetic valve or annuloplasty device in another position or requires replacement or repair of the mitral, pulmonary or tricuspid valve
- 2. Patient has had previous implant and then explant of the Model 400 aortic valve bioprosthesis
- 3. Patient presents with active endocarditis, active myocarditis, or other systemic infection

Revision 7.0

Page 7 of 22

Medtronic

- 4. Patient has an anatomical abnormality which would increase surgical risk of morbidity or mortality, including:
 - Ascending aortic aneurysm or dissection repair requiring circulatory arrest
 - Acute Type A aortic dissection
 - Ventricular aneurysm
 - Porcelain aorta
 - Hostile mediastinum
 - Hypertrophic obstructive cardiomyopathy (HOCM)
 - Documented pulmonary hypertension (systolic >60mmHg)
- 5. Patient has a non-cardiac major or progressive disease, with a life expectancy of less than 2 years. These conditions include, but are not limited to:
 - Child-Pugh Class C liver disease
 - Terminal cancer
 - End-stage lung disease
- 6. Patient has renal failure, defined as dialysis therapy or GFR<30 mL/min/1.73 m2.
- 7. Patient has hyperparathyroidism
- 8. Patient is participating in another investigational device or drug trial or observational competitive study
- 9. Patient is pregnant, lactating, or planning to become pregnant during the trial period
- 10. Patient has a documented history of substance (drug or alcohol) abuse
- 11. Patient has greater than mild mitral valve regurgitation or greater than mild tricuspid valve regurgitation as assessed by echocardiography
- 12. Patient has systolic EF<20% as assessed by echocardiography
- 13. Patient has Grade IV Diastolic Dysfunction
- 14. Patient has documented bleeding diatheses
- 15. Patient has had an acute preoperative neurological deficit or myocardial infarction and has not returned to baseline or stabilized ≥30 days prior to enrollment
- 16. Patient requires emergency surgery

6. Determination of Sample Size

Sample size for this trial was based on the safety objective. Sample size calculations were not performed for the effectiveness objective.

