7.9.2.2 Hypothesis

No formal hypothesis will be evaluated for this objective. Control articles based on current literature of previously approved heart valves will be selected. Data from the control articles will be provided so as to inform the reader of the current state of heart valve technology, as expressed by articles in guality peer-reviewed journals, and allow evaluation of the Model 400 data.

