7.9.2.3 Data Collection and Analysis Methods

NYHA functional classification and hemodynamic data will be summarized using descriptive statistics for continuous variables and frequency tables for discrete variables.

NYHA functional class will be evaluated based on the percentage of subjects in each specific NYHA class at each postoperative time-point and the percentage of subjects at each postoperative time-point who have improved, worsened, or not changed in NYHA class compared to preoperative baseline.

Medtronic PERIGON Pivotal Trial Statistical Analysis Form Plan Revision 7.0 Page 20 of 22 Medtronic

All echocardiograms will be analyzed by an echo core lab which will determine the values for the Hemodynamic Performance endpoints. Valvular regurgitation will be summarized with a frequency table for each visit interval and the other Hemodynamic Performance endpoints will be summarized as with continuous data. For each subject with paired data, the change from baseline may also be calculated at discharge (or 30 days), 3-6 months, 1 year and annually thereafter through 5 years. These data will be summarized by valve size.

Control articles based on current literature of previously approved heart valves will be selected. Effectiveness data from the control articles will be provided so as to inform the reader of the current state of heart valve technology, as expressed by articles in quality peer-reviewed journals, to allow for evaluation of the Model 400 valve effectiveness data.

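### The NYHA-by-gender comparison uses a plain chi-squared test that ignores class order and baseline class, so it gives up power and can carry a baseline difference forward

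*SAP*

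**What the plan says.** The gender analysis of effectiveness (SAP 7.9.3.2.2) plans a summary of NYHA class by gender and visit, and then a test: "The chisquared test will be used to evaluate the possible relationship between NYHA classification and gender at different time intervals". The section names no ordinal or trend version of the test, no rule for sparse cells or for combining classes, no adjustment for baseline and no significance level. The nearest threshold, "Differences in gender will be considered to be significant if the p-value<0.05", belongs to the safety gender analysis in SAP 7.9.3.1.2.

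Protocol 6.2 describes NYHA as "a system for defining cardiac disease and related functional limitations into four broad categorizations", and its Table 3 runs from no limitation (class I) to symptoms possible even at rest (class IV). Protocol 7.1.2.1 lists the assessments: "NYHA Functional Classification (at discharge (up to 30 days), 3-6 months, 1 year and annually thereafter through 5 years". That is seven post-operative time points.

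Baseline NYHA is a required assessment (Protocol 4.2 and 4.3). SAP 7.9.2.3 summarises "the percentage of subjects at each postoperative time-point who have improved, worsened, or not changed in NYHA class compared to preoperative baseline", for all subjects together and not by gender. For effectiveness the SAP states "No formal hypothesis will be evaluated for this objective" (7.9.2.2) and "Sample size calculations were not performed for the effectiveness objective" (Section 6).

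**The concern.** A Pearson chi-squared test on a 2 x 4 table has 3 degrees of freedom and gives the same p-value if the four classes are put in any other order. A tendency for one gender to sit in worse classes is a one-directional difference, and a test that spreads its sensitivity over all patterns is weaker against it. The SAP itself treats the scale as ordered elsewhere, since subjects can only be counted as those "who have improved, worsened, or not changed in NYHA class compared to preoperative baseline" if the classes have an order.

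The test also compares the genders at each visit without regard to where they started. If women enter surgery in worse classes than men, a difference at one year may be the pre-operative difference carried forward. The SAP already uses preoperative NYHA class as a covariate in its pooling and risk-factor models (7.3 and 7.9.3.1.3), so leaving it out here is not for lack of data.

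Protocol 7.3.3 commits to examining the endpoints for gender differences, and this is the only gender test of an effectiveness endpoint in the SAP. What is at stake is whether that comparison can find a real difference and whether its result can be read as one in functional recovery.

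**Working it through.** The plan gives no power figure for this test, so there is nothing to reproduce. It also gives no gender split, NYHA distribution or number per visit. Those inputs are assumed below and varied. The level is assumed to be two-sided 0.05.

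**1. Degrees of freedom.** (2 - 1) x (4 - 1) = 3 for the plain test, against 1 for an ordinal test. An effect with noncentrality 7.849 gives 80% power on 1 df and 64% on 3 df.

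**2. Power, base case.** Assume 750 men and 250 women, with 72/24/3.5/0.5% in classes I to IV, and a proportional-odds shift of women towards worse classes. For class I the odds in men are 0.72/0.28 = 2.571. At an odds ratio of 1.5 the odds in women are 2.571/1.5 = 1.714, so their class I share is 1.714/2.714 = 63%. Simulated power, as the range over repeated runs:

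| Odds ratio | Plain chi-squared | Ordinal rank test |
|---|---|---|
| 1.4 | 45-46% | 58-59% |
| 1.5 | 60-63% | 74-78% |

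**3. Power, other inputs.** At an odds ratio of 1.5, N from 600 to 1,300, 25% or 35% women, and class shares of 70/27/2.7/0.3, 80/18/1.8/0.2 or 60/33/6/1% (4,000 tables per setting), the plain test has power 37-87% and the ordinal test 46-94%. Examples:

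- N = 1,300, 35% women, 60/33/6/1%: 87.0% v 94.4%, a gain of 7.4 points (the smallest).
- N = 600, 35% women, 60/33/6/1%: 52.5% v 67.9%, a gain of 15.4 points (the largest).

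**4. Sparse cells and type I error.** In the base case with no gender difference, the expected class IV count is 250 x 0.005 = 1.25 in women and 750 x 0.005 = 3.75 in men. More than 99% of simulated tables had an expected count below 5. In the settings of step 3, the expected class IV count in women runs from 600 x 0.25 x 0.002 = 0.3 to 1,300 x 0.35 x 0.01 = about 4.5. Even so, the plain test rejected a true null in 3.8-4.9% of tables at N 600-1,300, and in 3.5-5.3% when N of 150 and 300 are included (Monte Carlo standard error about 0.3 points).

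**5. Baseline class.** In a second simulation (6,000 tables per setting, 25% women, N 600-1,300), follow-up class depended on baseline class only, so gender had no effect given baseline. Rejection by the planned test:

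- same baseline in both genders: 4.9-5.1%;
- women start worse, baseline odds ratio 1.5 to 2: 7-15%;
- women start worse, baseline odds ratio 3: 17-32%.

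**6. The stratified test itself.** In a further run on assumed inputs, an ordinal test stratified by baseline class kept the power gain (74% against 58% for the planned test). At a baseline odds ratio of 2 with no gender effect given baseline, it rejected in about 5%, where the planned test rejected in 14%.

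**The case against.** The strongest reply is that nothing rests on this test. It sits under additional analyses, for an objective with no formal hypothesis and no sample size calculation, and its section sets no threshold. The by-gender frequency table will show the class distributions whatever the p-value, and the SAP introduction expects analyses beyond the plan. This stands, and it limits the point to a free improvement.

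A second reply is that the SAP asks about the crude association between class and gender at each visit, not about recovery. For that question, omitting baseline does not invalidate the test. This also stands: the baseline issue concerns how a significant result is read. The documents give no evidence that men and women differ at baseline, so the 7-15% is conditional on that assumption.

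A third reply is that the power figures rest on assumed inputs and on a proportional-odds shift, the pattern that favours an ordinal test. That is fair. The direction held in every setting tried, but the size is not a property of this trial.

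A reader might also infer that nearly empty cells make the planned test invalid. The documents do not support that. They give no NYHA distribution, so sparse cells are plausible but not established, and where sparse tables were simulated the type I error stayed near or slightly below 5%.

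**Conclusion.** The planned test is valid for a crude association but inefficient for an ordered scale, and it does not separate a post-implant gender difference from one present before surgery. Under the assumed inputs, the loss against an ordinal test is about 14 points at an odds ratio of 1.4 with 750 men and 250 women, and 7 to 15 points at 1.5 over N 600-1,300. If the genders differ at baseline by an assumed odds ratio of 1.5 to 2, the crude test rejects in about 7-15% of cases with no gender effect given baseline. Reading the chi-squared test as Pearson's on all four classes is the natural interpretation, but the SAP does not name the variant. The matter is minor, and no primary safety or effectiveness conclusion depends on it.

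**What to change.** In SAP 7.9.3.2.2, replace the chi-squared sentence with an ordinal comparison at each visit that uses baseline class: either a test stratified by baseline NYHA class (Cochran-Mantel-Haenszel row-mean-score or van Elteren), or a proportional-odds model with gender and baseline NYHA as terms. Keep the frequency table by gender and visit so that the crude distributions stay visible, and label the result exploratory. It would help to state in the same place the significance level, if one is to be used, and what will be done if classes III and IV are sparse (an exact p-value or combining them), so that this is not decided after the data are seen.

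The cost is a sentence or two in the SAP and a standard procedure option. No new data are needed, because baseline NYHA is already collected.
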